SYNOPSIS

PROTOCOL AnticipUSC – N°ICO 2016-A-04

A) Clinical Trial Identification

TITLE OF THE TRIAL: *Multicenter, open-label, randomized study comparing early postoperative prophylactic non-invasive ventilation in the intensive care unit versus standard postoperative follow-up in patients at high risk of postoperative pulmonary complications according to the preoperative ARISCAT score, undergoing surgery under general or regional anesthesia (ANTICIPUSC)*

SHORT TITLE: ANTICIPUSC

COORDINATOR: [name] [name]

ESTIMATED NUMBER OF CENTERS: 3

NUMBER OF PATIENTS: 266

B) Sponsor Identification

NAME OF THE ORGANIZATION: ICO, DRCI-Cellule de Promotion

CONTACT PERSON: MME [name]

[contact]

[contact]

C) General Information About the Trial

Indication:

This study will focus on a selected population at high risk of postoperative pulmonary complications (PPC) according to the ARISCAT score, among all surgical patients in the participating centers, whether undergoing surgery under General Anesthesia (GA) or Regional Anesthesia (RA), who may benefit from preventive postoperative management.

Primary objective:

The primary objective of the study is to compare the effectiveness of a preventive postoperative management strategy using non-invasive ventilation (NIV) in the intensive care unit versus standard care, on the incidence of acute respiratory failure within 7 postoperative days during hospitalization, in patients at high risk according to the ARISCAT score.

Secondary objectives:

- The safety and tolerability of the strategy under study
- The cause of acute respiratory failure (arf) among the different postoperative pulmonary complications (ppc)
- Mortality during hospitalization for surgery, up to a maximum of 7 days
- Any effect on patient reintubation (cause and timing)
- Any effect on the length of stay in the icu/intensive care unit and on invasive or non-invasive mechanical ventilation
- Any effect on the incidence of healthcare-associated infections, defined according to the centers for disease control (cdc) criteria.

Inclusion criteria:

1. Patient aged 18 years or older
2. Patient scheduled for elective surgery or considered semi-urgent (pre-anesthesia consultation < 48 hours before the surgical procedure), under General Anesthesia (GA) or Regional Anesthesia (RA)
3. Patient with an ARISCAT score greater than or equal to 45 (high risk of PPC)
4. Written informed consent signed by the patient
5. Patient affiliated with a social security system

Exclusion criteria:

1. Minors, pregnant or breastfeeding women
2. Obstetric procedures
3. Surgeries under Local Anesthesia (LA) or peripheral nerve block
4. Procedures performed outside an interventional room (e.g., operating theater or interventional radiology)
5. Procedures related to previous surgical complications
6. Patients reoperated during follow-up (no double inclusion for the second surgery)
7. Organ transplantation
8. Patients already intubated preoperatively
9. Outpatient surgery
10. Refusal to participate or inability to provide informed consent
11. Persons deprived of liberty or adults under guardianship
12. Participation in another interventional study.

Primary endpoint:

Occurrence of acute respiratory failure (ARF) within 7 postoperative days during hospitalization, validated by the blinded adjudication committee with respect to the randomization arm.

Secondary endpoints:

Assessment of the safety and tolerability of the strategy under study:

- Discomfort or intolerance to NIV, defined as the inability to achieve the target of 6 to 8 hours per day due to premature termination of sessions caused by intolerance, despite proper implementation of NIV, including excessive leaks when these are the reason for stopping sessions
- Skin lesions at contact points between the interface and the patient's skin
- Anastomotic suture dehiscence (digestive or bronchial) when caused by a total pressure (PEEP + IPAP) > 20 cmH₂O
- Gastric distension defined as aeric distension of the gastric air pocket evidenced by imaging or gastric tube aspiration
- Occurrence of aspiration of secretions or vomit whose evacuation was hindered by the NIV mask

Any ARF must lead to investigation of its etiology using appropriate examinations:

Infectious pneumonia defined by a Modified Clinical Pulmonary Infection Score (CPIS) > 6, with microbiological thresholds of culture concentrations >10³ CFU/ml for a protected distal sample, >10⁴ CFU/ml for bronchoalveolar lavage, and >10⁶ CFU/ml for tracheal aspiration

The Modified Clinical Pulmonary Infection Score (modified CPIS)

CPIS Points	0	1	2
Tracheal secretions	Rare	Abundant	Abundant + purulent
Chest X-ray infiltrates	No infiltrate	Diffused	Localized
Temperature, °C	≥36.5 and ≤38.4	≥38.5. and ≤38.9	≥39 or ≤36.4
Leukocytes count, per mm ³	≥4,000 and ≤11,000	<4,000 or >11,000	<4,000 or >11,000 + band forms ≥500
P _{aO₂} /F _{IO₂} , mmHg	>240 or ARDS		≤240 and no evidence of ARDS
Microbiology	Negative		Positive

Figure 1 - Score CPIS

- Upper airway obstruction (aspiration or pulmonary congestion, altered consciousness defined by a Glasgow score ≤ 12)
- Heart failure with hydrostatic pulmonary edema
- Pulmonary embolism confirmed by contrast-enhanced pulmonary imaging during the arterial phase, or venous thrombosis confirmed and associated with ARF
- Pleural effusion: on chest X-ray, obliteration of the costophrenic angle or Damoiseau line in upright position, evidence of displacement of adjacent anatomical structures, opacity in one hemithorax with preservation of vascular shadows, or confirmed by thoracic CT scan
- Atelectasis: pulmonary opacity with mediastinal, hilar, or diaphragmatic shift toward the affected area and compensatory hyperinflation of the non-atelectatic lung, or confirmed by thoracic CT scan showing areas of atelectasis or derecruitment
- Pneumothorax: presence of air in the pleural space without vascular bed adjacent to the visceral pleura
- Bronchospasm: onset of expiratory wheezing treated with bronchodilators
- Aspiration pneumonia: pneumonia following inhalation of regurgitated gastric fluid
- Other etiology (e.g., other surgical complications)

- Upper airway obstruction (aspiration or pulmonary congestion, altered consciousness defined by a Glasgow score ≤ 12)
- Heart failure with hydrostatic pulmonary edema
- Pulmonary embolism confirmed by contrast-enhanced pulmonary imaging during the arterial phase, or venous thrombosis confirmed and associated with ARF
- Pleural effusion: on chest X-ray, obliteration of the costophrenic angle or Damoiseau line in upright position, evidence of displacement of adjacent anatomical structures, opacity in one hemithorax with preservation of vascular shadows, or confirmed by thoracic CT scan
- Atelectasis: pulmonary opacity with mediastinal, hilar, or diaphragmatic shift toward the affected area and compensatory hyperinflation of the non-atelectatic lung, or confirmed by thoracic CT scan showing areas of atelectasis or derecruitment
- Pneumothorax: presence of air in the pleural space without vascular bed adjacent to the visceral pleura
- Bronchospasm: onset of expiratory wheezing treated with bronchodilators
- Aspiration pneumonia: pneumonia following inhalation of regurgitated gastric fluid
- Other etiology (e.g., other surgical complications)

Assessment of mortality during hospitalization for surgery

- Death from any cause during hospitalization for surgery

Assessment of an effect on patient reintubation:

- Reintubation due to respiratory failure (ARF)
- Reintubation due to non-respiratory failure, excluding reintubations specifically for a new surgical or interventional radiology procedure
- Time to reintubation to assess delayed reintubation (characterized by a non-significant difference in reintubation rate between groups but a longer delay in the NIV group)

Assessment of an effect on length of stay in ICU and duration of invasive or non-invasive mechanical ventilation:

- Number of days of invasive mechanical ventilation (intubated or tracheostomized) during hospitalization for surgery, including episodes of reintubation
- Number of days of non-invasive mechanical ventilation (NIV) during hospitalization for surgery, including prophylactic and therapeutic NIV.

**Assessment of an effect on the incidence of healthcare-associated infections, defined according to
Centers for Disease Control (CDC) criteria:**

- Infectious pneumonia: see secondary endpoint criteria
- Urinary tract infection: fever $> 38^{\circ}\text{C}$ and urine culture showing no more than two microbial species, at least one with a concentration $> 10^5 \text{ CFU/ml}$, in a patient with no other obvious source of infection
- Catheter-related infection: fever $> 38^{\circ}\text{C}$, positive catheter culture or sample, and resolution of fever within 48 hours after catheter removal without antibiotic change and no other identified source of infection
- Bacteremia: fever $> 38^{\circ}\text{C}$ and at least one positive blood culture (two or more if coagulase-negative staphylococcus)
- Surgical site infection

Data collection is performed prospectively throughout the first 7 days of hospitalization for surgery.

D) Description of Investigational Medicinal Products

MEDICAMENTS :

Name of the Medicinal Product (INN)	Brand Name	Pharmaceutical Form	Route of Administration	Dosage per Administration
Medical Liquid Oxygen	N/A	Gas	N/A	

Therapeutic regimen:

The ventilatory mode used will be an assisted mode (PSV or BiPAP), as these have shown a stronger (86) and more sustained effect (29) than CPAP alone.

The interface—nasal mask, face mask, or helmet—is chosen according to the unit's usual practice.

NIV sessions of 1 hour are repeated every 2 to 3 hours, aiming for a daily assistance duration of 6 to 8 hours for a minimum of 24 hours. Weaning from NIV is managed by the clinician within a maximum of 48 hours.

Initially set between +5 and +8 cmH₂O, IPAP is gradually increased in increments of 2 to 3 cmH₂O for patient comfort, until achieving an inspiratory peak allowing an expired tidal volume (Vte) between 6–8 ml/kg of predicted body weight, according to current ventilation recommendations (84, 112), with a respiratory rate $< 30/\text{min}$.

PEEP is set between +5 and +10 cmH₂O, and FiO₂ adjusted to maintain SpO₂ $> 92\%$ or PaO₂ $> 70 \text{ mmHg}$ on blood gas analysis. Care is taken to ensure that total pressure (PEEP + IPAP) remains $\leq 20 \text{ cmH}_2\text{O}$ to avoid gastric distension (airway pressure lower than the lower esophageal sphincter pressure) (42) and to minimize the theoretical risk of bronchial suture dehiscence in thoracic surgery.

The ventilator's inspiratory trigger is set to the minimum value allowing the most sensitive detection of inspiratory efforts without causing auto-triggering.

The clinician may adjust IPAP based on the patient's blood gas results.

Duration of Treatment:

Each prophylactic NIV session lasts 1 hour. Sessions are repeated every 2 to 3 hours, separated by 2-hour periods without assisted ventilation to allow the patient to rest, eat, and receive care, including physiotherapy sessions. This schedule may be adapted to the unit's activity, with the goal of achieving a daily assistance duration of 6 hours without exceeding 8 hours, for a minimum of 24 hours.

Weaning from NIV is managed by the clinician within a maximum of 48 hours.

Expected outcomes:

Prevent the occurrence of PPCs and the complications they cause:

- Infectious pneumonia and aspiration pneumonia
- Pleural effusions
- Atelectasis
- Bronchospasm
- Acute respiratory failure (ARF) and hypoxemia, and consequently:
 - Prevent patient reintubation
 - Prevent surgical site infections and anastomotic suture dehiscence
 - Reduce morbidity and mortality related to reintubation, and shorten length of stay
 - Avoid the need for invasive mechanical ventilation and all associated complications:
 - Nosocomial infections, including ventilator-associated pneumonia (VAP) due to micro-aspirations linked to the endotracheal tube
 - Delayed rehabilitation
 - Communication difficulties
 - Discomfort

E) CONSIDERATIONS STATISTIQUES

Statistical analyses will be performed using R software and IBM SPSS.

A total of 266 patients are planned for inclusion, divided into two balanced groups.

DESCRIPTION OF PLANNED STATISTICAL METHODS:

Research Protocol

Patients will be analyzed on an intention-to-treat basis and then per-protocol.

Intention-to-treat analysis: all patients included in the study for whom outcome data are available will be considered in the analysis according to their randomization group. No imputation method will be used in case of missing data.

If organizational constraints prevent the patient from receiving prophylactic NIV (despite inclusion in the corresponding intervention arm), the patient will remain in their randomization arm for the entire study duration, and their data will be analyzed on an intention-to-treat basis.

Per-protocol analysis excludes patients for whom the initial protocol was not fully adhered to. Only patients who followed the protocol will be considered in the analyses, within the arm to which they were originally randomized.

The analysis will focus on the primary endpoint to determine whether randomization to the "PPC prevention strategy" arm leads to a reduction in PPC frequency compared to the control group. Effect size and number needed to treat will be calculated.

Similarly, for secondary endpoints, significant differences between the two groups will be sought in terms of:

- a) Safety and tolerability of the strategy under study (see safety assessment parameters)
- b) Mortality during hospitalization
- c) Patient reintubation
- d) Length of stay and duration of invasive or non-invasive mechanical ventilation

Description of the overall analysis method

The significance threshold is set at 0.05, and all tests will be two-sided. For qualitative variables, results will be reported as counts and percentages. For quantitative variables, results will be reported as means and standard deviations in case of normal distribution, and as medians with 25th and 75th percentiles in the absence of a Gaussian distribution. Normality of continuous variables will be assessed using the Kolmogorov-Smirnov test.

A simple descriptive analysis will be performed on the entire study population and by subgroups. This description will include sociodemographic data, medical history, ongoing treatments, etc.

A qualitative and quantitative analysis of missing data will be performed. No imputation of missing data is planned for the endpoints.

Study of Associations (Qualitative and/or Quantitative Variables):

For each parameter of interest, a bivariate analysis will be performed, possibly complemented by a multivariate analysis adapted to the outcome variable to explore potential associations.

For bivariate analyses, the use of parametric or non-parametric tests will depend on sample size and/or variable distribution. The significance threshold is set at 0.05, and all tests will be two-sided.

The statistical test used will be Pearson's Chi-square test (or Fisher's exact test) for qualitative variables. For quantitative variables, the statistical tests used will be ANOVA or the non-parametric Kruskal-Wallis test.

The association between each presumed risk factor and the parameter of interest will be estimated using the relative risk (RR) and its 95% confidence interval.

A multivariate logistic regression analysis will estimate the adjusted RR and its 95% confidence interval for each retained factor (conservative threshold of 0.20 in univariate analysis).

Early Mortality:

Overall survival is defined as the time between the date of operating room discharge and the date of death if the patient dies within 7 days, or the end of study follow-up at Day 7. The Kaplan-Meier method will be used to estimate survival rates and plot survival curves. The Log-Rank test will be used to compare survival curves. Event-free survival is defined as the time between operating room discharge and the date of occurrence of the event (PPC) or the date of last follow-up if censored.

A semi-parametric Cox proportional hazards regression model will estimate for each variable the crude association (Hazard Ratio, HR) between the factor studied and death (bivariate analysis), then the adjusted HR in multivariate analysis.

The significance threshold for including other variables in the multivariate analysis will be 0.20. If several candidate variables are redundant, the most representative variable will be retained for the model.

Subgroup Analyses (Exploratory):

Subgroup analyses will address the occurrence of endpoints:

- According to patient characteristics at inclusion (medical history, ARISCAT score components, type of surgery, and planned anesthetic technique).
- The subgroup of patients receiving NIV as curative (under conditions noted at session start) will be compared to the group receiving NIV only prophylactically in terms of outcome at Day 7.
- Identification of factors associated with failure of prophylactic NIV in the subgroup where NIV was prematurely discontinued.

Statistical Justification for Sample Size:

Previously described data indicate that the expected effect size is approximately a 50% reduction in events:

- In studies on medical populations, the effect of prophylactic NIV was observed even on harder endpoints than ours: -66% reduction in reintubation, -51% reduction in ARF incidence, and -50% reduction in reintubations, and again -69% reduction in ARF incidence.

- In surgical populations, prophylactic NIV has led to a reduction in restrictive syndrome of about 50%, an improvement in pulmonary function tests (PFTs) of +30%, and a decrease in length of stay by 7 days.
- In curative use after abdominal surgery—a more unfavorable situation since ARF is more advanced—Squadrone reported favorable outcomes in 90% of cases with CPAP, and reintubations were reduced by 30%.

Given that the expected incidence of ARF in the high-risk group is 30–50%, a sample size of at least 121 subjects per arm is required to demonstrate, under a two-sided hypothesis, a relative reduction of 50% in ARF between a group managed with prophylactic NIV (15%) and a group managed with standard care (30%), with an alpha risk of 5% and a beta power of 90%. We anticipate 10% of patients will be non-evaluable.

The required sample size is therefore $242 + 24 = 266$ high-risk subjects evaluated for PPC.

STATISTICAL STOPPING RULES:

No interim analysis is planned in the protocol. However, if during the review of safety and efficacy data provided to the independent monitoring committee (raw, descriptive, and summarized data without pre-established statistics by the investigator or sponsor), a highly significant difference is identified for the primary endpoint or one of the safety parameters when comparing the two groups blinded to treatment allocation, the committee may decide to stop the study.

METHOD FOR HANDLING MISSING, UNUSED, OR INVALID DATA:

Patients included in the study for whom an endpoint is not available will not be considered in the analysis for that missing endpoint. No imputation method will be used for missing data.

MANAGEMENT OF CHANGES TO THE INITIAL ANALYSIS PLAN:

Modifications to the initial analysis plan may be proposed by the monitoring committee (interim analysis, statistical tests, adverse events, secondary objectives) if new literature data justify them.

Protocol deviations will be identified and measured. Dual analysis—intention-to-treat and per-protocol—will assess the impact of protocol deviations on study results.

SELECTION OF PATIENTS FOR ANALYSIS:

All patients included in the study, meeting all inclusion criteria and presenting no exclusion criteria, will be included in the analyses of available endpoints according to their case report forms.

See Criteria for Premature Discontinuation of a Participant's Involvement in the Study:

- **Withdrawal of consent:** Data collected will not be included in the intention-to-treat analysis.
- **Discontinuation by the investigator:** Data already collected will be used in the analyses unless the subject withdraws consent.
- **Lost to follow-up:** Data collected for subjects lost to follow-up will be used in the analyses unless the subject withdraws consent.
- **Organizational impossibility to receive prophylactic NIV (inclusion in the corresponding intervention arm):** The patient will be included in the intention-to-treat analysis and followed under the same conditions as in the control arm.

RANDOMIZATION

High-risk patients with an ARISCAT score ≥ 45 will be randomized upon inclusion in the study during the preoperative period (consultation or pre-anesthesia visit, and no later than the day of surgery before anesthesia begins).

Treatment allocation will be performed through centralized computerized electronic randomization by minimization into two groups (1:1), with stratification by center, sex, age, preoperative SpO₂, presence of respiratory infection within the previous month, anemia, surgical incision (upper abdominal or intrathoracic), expected surgery duration (≤ 2 h, 2–3h, > 3 h), and procedure urgency.

F) Planned Duration of the Trial

Inclusion period:	30 months
Treatment period:	48 hours
Follow-up period:	7 days
Total duration of the trial (including follow-up):	30.5 months

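### Exclusion criterion 6 names an event after randomization and, read with the analysis-selection rule, can be taken to drop reoperated patients, which conflicts with the intention-to-treat definition

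*Combined protocol and SAP*

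**What the plan says.** All references are to the combined protocol and SAP.

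- **Section C, Exclusion criteria, item 6:** "Patients reoperated during follow-up (no double inclusion for the second surgery".
- **Section E, Randomization:** "High-risk patients with an ARISCAT score ≥ 45 will be randomized upon inclusion in the study during the preoperative period", and at the latest on the day of surgery before anesthesia starts.
- **Section E, Selection of patients for analysis:** the rule reads "All patients included in the study, meeting all inclusion criteria and presenting no exclusion criteria, will be included in the analyses of available endpoints".
- **Section E, Description of planned statistical methods (intention-to-treat):** "all patients included in the study for whom outcome data are available will be considered in the analysis according to their randomization group". The same paragraph adds: "No imputation method will be used in case of missing data".
- **Section C, reintubation endpoint:** reintubation for non-respiratory failure is counted "excluding reintubations specifically for a new surgical or interventional radiology procedure".
- **Section C, safety endpoints:** "Anastomotic suture dehiscence (digestive or bronchial" is listed, but only when a total pressure above 20 cmH₂O caused it.

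The list of participant-discontinuation situations in section E covers consent withdrawal, discontinuation by the investigator, loss to follow-up and organizational impossibility of giving NIV. Reoperation is not on it. No sentence says that reoperated patients are kept.

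**The concern.** An exclusion criterion should be decidable when the patient is entered. Reoperation during follow-up is not, because randomization precedes the first operation. The criterion would do no harm if it governed enrolment alone. The selection paragraph, however, carries the exclusion criteria into the definition of who is analyzed, and so gives a postoperative event the power to remove a randomized patient.

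The plan itself ties that event to outcome and possibly to treatment. It lists other surgical complications among the causes of ARF. It lists suture dehiscence as a possible harm of NIV and, under Expected outcomes in section D, as something NIV should help prevent. Reoperation could therefore differ between arms in either direction, and reoperated patients may well have a higher risk of ARF. Dropping them would replace a randomized comparison with a comparison of survivors of a selection step. The trial is also open-label, so whoever decides between the two readings could know the arm.

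**Working it through.** **Step 1. Which texts remove and which retain.**

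| Text | Effect on a randomized patient reoperated on, say, Day 3 |
|---|---|
| Exclusion item 6, main phrase | Meets an exclusion criterion |
| Exclusion item 6, parenthesis | Only not enrolled a second time |
| Selection of patients for analysis | Out, if item 6 is met |
| Intention-to-treat definition | In, by randomized arm, if outcome data exist |
| Reintubation endpoint | In: a carve-out for new surgery is needed only if such patients are still followed |
| Discontinuation list | Not mentioned, so no instruction to withdraw |

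The selection paragraph and the intention-to-treat definition give opposite answers for the same patient, and no rule says which prevails.

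**Step 2. What removal would do to the primary comparison.** The plan has no figure to reproduce here. Inputs from the plan: 266 patients allocated 1:1 (133 per arm), control ARF 30%, planned NIV ARF 15%. Assumed, because the documents are silent: the share reoperated in each arm (r) and the ARF risk among reoperated patients (q).

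If p is the ARF risk in the whole arm, the risk left after removal is (p − r·q) / (1 − r).

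*No true effect, p = 30% in both arms:*

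- r = 8% NIV and 5% control, q = 50%. NIV: (0.30 − 0.040)/0.92 = 28.3%. Control: (0.30 − 0.025)/0.95 = 28.9%. Risk ratio 0.976. Patients removed: 133 × (0.08 + 0.05) ≈ 17.
- r = 10% NIV and 5% control, q = 60%. NIV: (0.30 − 0.060)/0.90 = 26.7%. Control: (0.30 − 0.030)/0.95 = 28.4%. Risk ratio 0.938. Patients removed: 133 × (0.10 + 0.05) ≈ 20.

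By normal approximation, with 121 to 133 per arm before removal, the nominal 5% two-sided test rejects about 5.2% of the time in the first case and 6.0–6.1% in the second.

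*Direction reversed*, r = 5% NIV and 10% control, q = 60%: 28.4% against 26.7%, risk ratio 1.07, so the bias goes against NIV.

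*Equal r and equal q:* the two arms shrink alike and the null risk ratio stays at 1.00.

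*Planned effect (30% against 15%, true ratio 0.50)*, r = 5% in both arms and the same q in both:

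- q = 50%: (0.15 − 0.025)/0.95 = 13.2% against 28.9%, ratio 0.45.
- q = 90%: (0.15 − 0.045)/0.95 = 11.1% against (0.30 − 0.045)/0.95 = 26.8%, ratio 0.41.

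So if NIV works but does not lower ARF among reoperated patients, even balanced removal makes the benefit look larger.

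**The case against.** The best defence is that item 6 states its own purpose. The parenthesis speaks only of double inclusion, and several neighbouring items describe procedures rather than patients, so item 6 can be read as saying that a second operation is not a new inclusion. The intention-to-treat definition, the reintubation endpoint and the silence of the discontinuation list all fit retention. This stands, and it makes a bar on re-enrolment the likelier intent. It does not settle the matter, because the phrase that is excluded is the reoperated patient, and the selection paragraph applies exclusion criteria to the analysis without limiting them to those known at entry.

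Three stronger readings are tempting, and the documents do not support them:

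- **That sites will withdraw or screen-fail reoperated patients.** No text tells them to. The selection paragraph is a rule about analysis.
- **That the bias is large or favours NIV.** The illustration gives 0.94–0.98 against a planned ratio of 0.50, and the direction reverses if control patients are reoperated more often. More extreme assumptions give more: 15% against 5% reoperated with 90% ARF among them gives (0.30 − 0.135)/0.85 = 19.4% against 26.8%, ratio 0.72. Nothing in the documents points to such rates.
- **That the dehiscence safety endpoint would be emptied.** It counts only cases attributed to a total pressure above 20 cmH₂O, while the NIV regimen in section D keeps total pressure at or below that value. Few cases may qualify whatever happens to reoperated patients, and the documents allow no estimate of the loss.

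**Conclusion.** Wrong as written, as an internal inconsistency, with moderate confidence. It is certain from the text that item 6 names an event that can only follow randomization, and that the selection paragraph and the intention-to-treat definition disagree about a patient who has it. It is not certain that anyone would be removed. A reader might infer that the plan does remove these patients, but the text supports only that it can be read that way.

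If the literal rule were applied, about 17–20 of 266 patients would go under the illustrative rates, and a true risk ratio of 1.00 would read 0.94–0.98. Those figures rest wholly on assumed reoperation rates and an assumed ARF risk after reoperation. The case for acting rests on the broken randomized comparison and on leaving the choice of reading open until data are in hand, more than on the size of the illustrated bias.

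**What to change.** 1. **Exclusion item 6:** reword as a bar on second inclusion only. For example: a reoperation, during follow-up, of a patient already in the study does not count as a new inclusion. Keep the scope to the follow-up period, as the present text does. A lifetime bar on re-entry would be a different and wider rule.
2. **Selection of patients for analysis:** limit the exclusion-criteria condition to criteria that can be assessed before randomization.
3. **Same paragraph:** state that a randomized patient who is reoperated stays in the allocated arm, is followed to Day 7 from the index operation, and is counted for all endpoints, in line with the intention-to-treat definition.

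The cost is a few sentences, with no extra patients or visits and no change to clinical management. If only re-enrolment was ever meant, the sponsor loses nothing by saying so.

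### The dehiscence safety endpoint counts only events caused by PEEP + IPAP above 20 cmH₂O, a range the regimen aims to avoid, so it cannot show dehiscence under the strategy as planned

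*Combined protocol and SAP*

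**What the plan says.** Section C makes "The safety and tolerability of the strategy under study" a secondary objective. Among its safety endpoints is "Anastomotic suture dehiscence (digestive or bronchial) when caused by a total pressure (PEEP + IPAP) > 20" cmH₂O.

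Section D, Therapeutic regimen, deals with the same sum: "Care is taken to ensure that total pressure (PEEP + IPAP) remains" at or below 20 cmH₂O, partly because of a theoretical risk to bronchial sutures in thoracic surgery. Expected outcomes, in the same section, lists prevention of anastomotic dehiscence among the hoped-for benefits.

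Section E, Description of planned statistical methods, looks for significant differences between the two groups in safety and tolerability. Statistical stopping rules lets the monitoring committee stop the study on a marked difference in a safety parameter.

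Blinded review is stated only for the primary endpoint, ARF: "validated by the blinded adjudication committee with respect to the randomization arm". On timing, "Data collection is performed prospectively throughout the first 7 days of hospitalization for surgery".

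Two further rules bear on who is analysed. Exclusion criterion 6 reads "Patients reoperated during follow-up (no double inclusion for the second surgery"), and Selection of patients for analysis keeps included patients "meeting all inclusion criteria and presenting no exclusion criteria".

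**The concern.** The endpoint starts counting where the regimen is meant to stop. It therefore cannot describe dehiscence under the strategy being tested, either as the harm that the regimen section mentions or as the benefit listed under Expected outcomes. A count of 0 or close to 0 could be taken as reassurance when it only reflects the definition.

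The few events that might qualify depend on a judgement that pressure caused the dehiscence. The trial is open-label, no criteria for that judgement are given, and the blinded committee is assigned only to ARF. Randomisation makes an all-cause comparison possible without any such judgement, and the current definition gives that up.

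A smaller point concerns reoperation. Read literally, exclusion 6 together with the analysis-selection rule could remove patients reoperated for dehiscence. The parenthesis in exclusion 6 suggests that it only bars a second inclusion, but the text does not settle the matter.

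**Working it through.** The plan gives no dehiscence rate and no power for this endpoint, so there is no figure to reproduce. The check has four steps.

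**1. Counted range against intended range.** The endpoint counts events caused by PEEP + IPAP > 20 cmH₂O; the regimen aims for ≤ 20. The ranges do not overlap.

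| Situation | Can a dehiscence be counted? |
|---|---|
| NIV arm, limit respected | No |
| NIV arm, limit exceeded | Only if judged to be caused by the pressure |
| Control without NIV | No, there is no PEEP + IPAP |
| Control given curative NIV above the limit | Only if judged to be caused by the pressure |

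Exceedance is possible but not intended. The highest starting settings give 8 + 10 = 18, and one 3 cmH₂O step gives 18 + 3 = 21.

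**2. Do other listed endpoints fill the gap?** Surgical site infection is a different event. "Other etiology (e.g., other surgical complications") is recorded only as a cause of ARF. The committee reviews safety data, but no other definition of dehiscence is given.

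**3. What the planned test would need.** Study of Associations allows Fisher's exact test. For k events against 0 in equal arms of n, the two-sided p-value is 2 × C(n, k) / C(2n, k). I use n = 121, the evaluable number per arm in the sample-size section, and n = 60 on the assumption that about half the patients have an anastomosis or suture at risk.

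| Counted events, NIV vs control | n = 121 | n = 60 |
|---|---|---|
| 4 vs 0 | 0.122 | 0.119 |
| 5 vs 0 | 0.060 | 0.057 |
| 6 vs 0 | 0.029 | 0.027 |

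At least 6 dehiscences would have to be attributed to pressures that the regimen aims to avoid.

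**4. What an all-cause count would give.** All rates here are assumptions. Power is the exact probability, summed over all pairs of binomial counts, that two-sided Fisher p ≤ 0.05.

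| Assumed rates (a doubling) | Power, n = 121 | Power, n = 60 |
|---|---|---|
| 2% vs 4% | 6% | 1% |
| 5% vs 10% | 22% | 9% |
| 10% vs 20% | 52% | 25% |

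At 5% vs 10%, expected events per arm are 121 × 0.05 = 6.1 and 121 × 0.10 = 12.1, or 3.0 and 6.0 with n = 60. The 95% CI half-width is 1.96 × √[(0.05 × 0.95 + 0.10 × 0.90) / n]:

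- n = 121: 1.96 × √(0.1375 / 121) = 6.6 points
- n = 60: 1.96 × √(0.1375 / 60) = 9.4 points

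Using all 133 randomised per arm (266 / 2) changes little: Fisher power at 5% vs 10% is about 26%.

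**The case against.** The strongest reply is that the safety list is mainly about harms specific to NIV. Mask intolerance, skin lesions under the interface and aspiration hindered by the mask cannot occur in a control without NIV either, so an attributable-harm definition of dehiscence fits the list. This has some force: leaving out control events is not an error in itself. It does not explain why NIV-arm events at the intended pressures are also left out. Dehiscence, unlike a mask lesion, also occurs without NIV, so it can be compared between arms.

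A second reply is that the text is a synopsis and that adverse-event reporting may capture other dehiscences. That may be so, and it limits the claim: the defect is certain for this endpoint, not for everything the trial might record. It would not mend the comparison in section E.

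A third is that the remedy is weak. Power is low, detection may differ between intensive care and standard follow-up, and the remedy adds no blinded assessment. These limits stand and should be stated. A wide interval on the relevant event is still more informative than a count held near zero by definition.

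Finally, data collection is described for the first 7 days of hospitalisation, so a patient discharged earlier may not be observed to Day 7. The 7-day follow-up in section F supports a Day 7 window, but the plan should say how early discharge is handled.

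**Conclusion.** The concern holds. If the pressure limit is respected, the endpoint returns 0 vs 0 at any true dehiscence rate. If it is sometimes exceeded, the endpoint counts only departures from the regimen, through an unblinded causal judgement, and would need at least 6 vs 0 to reach p ≤ 0.05.

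This should be fixed. It makes one named safety endpoint uninformative about a risk that the protocol itself raises, but it does not affect the primary endpoint or the sample size. The conclusion about the definition rests on the documents' text alone. The power and interval figures rest on assumed rates and, for n = 60, on an assumed share of patients at risk. The reoperation point is an ambiguity to clear up, not a separate defect.

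**What to change.** Redefine the endpoint along these lines: *any digestive or bronchial anastomotic or suture dehiscence diagnosed up to Day 7, recorded the same way in both arms regardless of ventilation pressure or cause.* In addition:

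- State that patients reoperated for dehiscence stay in this analysis and that exclusion 6 bars only a second inclusion.
- Report, by arm, the number of patients with a digestive or bronchial anastomosis or suture and, among them, the risk difference with its 95% CI, labelled as an estimate and not a powered test.
- Report the highest PEEP + IPAP where NIV was used, and any attribution to pressure, descriptively only. Label attribution as the unblinded investigator's opinion.
- State how patients discharged before Day 7 are handled, identically in both arms.

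The ventilation regimen is not changed.

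The cost is one definition, short clarifications on reoperation and early discharge, and a few case-report-form fields within the planned 7-day collection. Both arms need anastomosis or suture present, dehiscence yes/no, and date; where NIV was used, highest PEEP + IPAP and attribution. If the sponsor wants observation after an early discharge, that follow-up is an extra cost. The price in interpretation is a wide interval, a doubling that would probably be missed at control rates of 5% or less, and possible unequal detection between settings.
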